1.0 Study Synopsis

Objectives:

Primary:

1. To evaluate the safety of primary and boost vaccinations with lethally irradiated allogeneic pancreatic tumor cells transfected with the GM-CSF gene vaccine in the treatment of patients with surgically resected adenocarcinoma of the head, neck, or uncinate of the pancreas

Secondary:

1. To estimate the association of specific *in vivo* parameters of immune response including, but not limited to mesothelin, prostate stem cell antigen (PSCA), and mutated *k-ras*-specific T cell responses, with clinical responses in patients who are receiving semi-annual vaccine boosting with lethally irradiated allogeneic pancreatic tumor cells transfected with the GM-CSF gene.
2. To estimate the efficacy of vaccine boosts in the treatment of patients with adenocarcinoma of the pancreas in terms of overall and recurrence free survival.
3. To use the serum GM-CSF levels as a measure of longevity of an allogeneic vaccine following a semi-annual boosting with lethally irradiated allogeneic pancreatic tumor cells transfected with the GM-CSF gene.
4. To determine the psychosocial and symptom profiles of patients with pancreatic cancer treated with an irradiated allogeneic GM-CSF secreting vaccine, and to explore changes over time. The psychosocial profile will include information about, but is not limited to demographics, quality of life, hope, trust, social support, decision control and advanced directives. The symptom profile will include but is not limited to pain, anorexia, fatigue, and mood state.

Study population:

In order to be considered for this study, patients need to meet following major criteria for inclusion: History of surgically resected pathologic stage 1 (no direct tumor extension beyond pancreas and no regional lymph node metastases), 2 (direct extension of tumor beyond pancreas), and/or 3 (regional lymph node metastases) adenocarcinoma of the head, neck, tail, or uncinate of the pancreas.

Have no radiographic evidence of pancreatic cancer disease recurrence.

Have not received any anti-cancer therapy in the past 28 days.

Study Design:

Eligible subjects will receive by intradermal administration the pancreatic tumor vaccine consisting of two irradiated, allogeneic pancreatic tumor cell lines transfected with the granulocyte macrophage-colony stimulating factor (GM-CSF) gene. There will be two cohorts of research participants: those who have previously received the pancreatic cancer vaccine (up to 17) and those

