2.8.1 Preliminary Data

Sixty research participants received at least one and a maximum of five vaccinations of two pancreatic cancer cell lines each delivering 2.5×10^8 cells intradermally distributed among three lymph node regions in the Johns Hopkins study, IRB # 00-01-13-02 (SKCCC J9988) entitled, A safety and efficacy trial of lethally irradiated allogeneic pancreatic tumor cells transfected with the GM-CSF gene in combination with adjuvant chemoradiotherapy for the treatment of adenocarcinoma of the pancreas. See Table 2 for the demographic details. Vaccine one was administered 8-10 weeks following surgical resection. Patients were subsequently treated with 5-fluoruracil (5-FU) continuous infusion based chemotherapy integrated with radiotherapy. Research participants who remained disease-free one month after completing the chemoradiotherapy received the vaccines two through four one month apart. A fifth and final vaccine was administered six months after the fourth vaccine.

Table 2. Research Participants' Demographic Data

Characteristic	N=60
Male	37
Female	23
Median age	56.7
Age range	41-83
Node +	52
Margin +	18
Node + and Margin +	18

Enrollment was completed in January of 2005. At an early analysis, 56 patients were evaluable at one year and 36 patients were evaluable at two years. The one and two year survival rates are 88% and 76%, respectively. This data compares very favorably with the available published data.

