4.3.1 Efficacy endpoints

The primary efficacy endpoint of interest is the overall survival (OS) of patients treated with vaccine boosts. The overall survival is defined as the time from the first vaccine boost until death. If a patient is lost to follow-up or the study is ended prior to death, the patient will be considered censored at their last recorded follow-up. For each cohort, Kaplan Meier curves will be constructed and the median survival estimates will be calculated with 95% confidence intervals using Greenwood's formula. Since the time between completion of treatment and the initiation of vaccine boosts will vary among subjects, we will use a Cox proportional hazards model to adjust for this delay in boosts.

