We are also interested in investigating the effect of vaccine boosts on recurrence free survival (PFS). Patients who are treated at Johns Hopkins will be followed every 3 months and evaluated for recurrence. However, the standard of care follow-up varies from institution to institution. In order to prevent biasing our results, it is necessary to coarsen the follow-up interval so that every individual is evaluated at the same time points regardless of the institution. For example, if the only visits held in common among all patients were the semi-annual exams prior to vaccine boosting, it would be necessary to only consider the status of the JH patients at those two time points regardless of recurrence information gained from the additional 2 visits. This coarsening of the data may cause an overestimation of PFS. In order to take into account both potential forms of bias, we will perform our analysis of PFS on the entire cohort as well as the subpopulation of patients from Johns Hopkins (estimated to be approximately 50% of the research participants). PFS will be defined as the time from the first vaccine until evidence of disease recurrence. If a patient withdraws from the study prior to being diagnosed with progressive disease, they will be censored at the date of their last follow-up visit. If an individual dies prior to being diagnosed with progressive disease, they will be considered to have progressed at the date of their last follow-up visit. This is a conservative estimate if we count the disease recurrence at the next planned visit then this will bias the PFS time upward. The PFS will be summarized using Kaplan-Meier curves and estimates of median PFS with 95% confidence intervals based upon Greenwood's formula. Due to potential causes of bias discussed earlier, the results will be considered extremely preliminary. If the PFS estimates for patients treated at Johns Hopkins appear to be lower than that of the population as a whole and the Johns Hopkins patients are followed at more frequent intervals than the other patients, then this indicate that an overestimation of PFS may exist. No formal comparison is planned due to the small sample size. Such results could affect the future planning of follow-up treatment for patients in subsequent trials.

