5.0 Response Criteria

5.1 Evaluation of Clinical Activity

Most patients will have only minimal residual disease at the time of enrollment. Therefore, there will be no evaluable disease to measure at baseline. Patients will be monitored for disease-free and overall survival. The results from this trial will be compared to historical controls seen at the Johns Hopkins Hospital (5). Patients recently seen at the Johns Hopkins Hospital who can be matched for pathologic stage, surgical intervention, and adjuvant combination chemotherapy and radiation therapy, are the most accurate group of historical controls since our institution has the largest reported experience treating patients with this disease and has recently reported the best survival statistics for current interventions (5).

Patients may undergo standard of care evaluations consisting of abdominal, chest, and pelvis CT scans at regular intervals to evaluate for local recurrence and distant metastases. In addition, any patient presenting with symptoms will undergo evaluation for metastases. Recurrent disease is defined as evidence of either local or metastatic recurrence by CT scan.

The serum tumor marker CA19-9 lacks a sufficient sensitivity and specificity to serve as reliable indicators of response. The CA 19-9 levels will be followed to evaluate whether large and persistent changes might correlate with either in vitro immune responses or with time to clinical recurrence.

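### The plan asks for the efficacy of vaccine boosts, but its only efficacy comparator, historical controls not matched on vaccination, cannot separate boosts from the vaccine course before them

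*Combined protocol and SAP*

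**What the plan says.** Secondary objective 2 in the synopsis is "To estimate the efficacy of vaccine boosts in the treatment of patients with adenocarcinoma of the pancreas in terms of overall and recurrence free survival". Section 4.3.1 repeats the focus on boosts: "The primary efficacy endpoint of interest is the overall survival (OS) of patients treated with vaccine boosts", and "We are also interested in investigating the effect of vaccine boosts on recurrence free survival (PFS").

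The two endpoints start at different points: "The overall survival is defined as the time from the first vaccine boost until death", whereas "PFS will be defined as the time from the first vaccine until evidence of disease recurrence".

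Section 5.1 supplies the external comparator: "The results from this trial will be compared to historical controls seen at the Johns Hopkins Hospital (5"). It prefers recent patients of the same institution, matched on pathologic stage, surgery and adjuvant chemoradiation. Vaccination does not appear in that list, and neither does being recurrence free at a given time.

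Section 4.3 calls the secondary analyses mainly descriptive, and they are done separately for the two cohorts.

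**The concern.** A comparison isolates boosts only if the comparator had the same earlier vaccination and no boosts. Section 5.1 does not ask for that, and no such group is planned elsewhere. If the boosts added nothing, the comparison could still look favourable because of the earlier vaccine course, or because of selection into it. Section 4.3 intends these estimates to feed hypotheses for later trials, so an estimate labelled as boost efficacy would carry the wrong meaning forward. The caveats in section 4.3.1 concern visit frequency and the timing of recurrence; none covers this.

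**Working it through.** **No plan figure to reproduce.** The documents give no target effect, control rate or precision for efficacy. The figures in section 4.1 (exact lower bound 11.89% for 6 of 20; maximum interval widths 0.438 and 0.309) concern dose-limiting toxicity. They reproduce (11.893% by Clopper-Pearson; 0.4383 and, apart from truncation, 0.3099 by the normal approximation) and do not bear on this point.

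**Step 1: exposure by cohort, set against the objective.**

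| | Vaccine-naive | Previously vaccinated |
|---|---|---|
| Vaccine before first boost | Three monthly primes (synopsis, 3.4.1) | Phase I course (2.7.1) or one to five phase II vaccines (2.8.1) |
| Vaccine given on study | Primes, then boosts | Boosts only |
| Restriction at entry | At least 28 days after last anti-cancer therapy, no recurrence | No recurrence for at least 1 year after treatment (4.1) |
| OS clock | First boost, after the primes | First boost |
| PFS clock | First prime | First on-study vaccine, which is a boost (3.4.1.1) |
| Contrast with unvaccinated controls reflects | Primes plus boosts | Parent course plus boosts, plus selection for a recurrence-free year |

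In neither column is the contrast the effect of boosts alone.

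**Step 2: does anything else in the plan isolate boosts?** Both cohorts are boosted, so neither can act as an unboosted group. The Cox model in 4.3.1 adjusts for the delay before boosting, not for earlier vaccination. The Johns Hopkins subgroup analysis of PFS addresses how often patients are assessed.

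**Step 3: would landmarking cure it?** Requiring controls to be recurrence free at the same time point would deal with time at risk. It would leave the difference in treatment received.

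**Step 4: illustration.** Assume proportional hazards, multiplicative effects and unvaccinated controls. Then

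HR(observed) = HR(earlier course) × HR(boost).

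| HR, earlier course (assumed) | Observed, HR(boost) = 1.0 | Observed, HR(boost) = 0.8 |
|---|---|---|
| 0.9 | 0.90 | 0.72 |
| 0.8 | 0.80 | 0.64 |
| 0.7 | 0.70 | 0.56 |
| 0.5 | 0.50 | 0.40 |

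A vaccinated but unboosted comparator would return 1.0 and 0.8 in every row. The documents do not give the hazard ratio of the earlier course, so no row can be singled out.

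**The case against.** **The comparison is descriptive, and no boost claim is attached to it.** Section 5.1 gives it one sentence, with no model, test or decision rule, and speaks of the trial's results in general. Section 4.3.1 contains no historical-control analysis and treats its PFS results as very preliminary. The primary endpoint is safety. All of this stands and limits the weight of the point. It does not remove the mismatch between what objective 2 asks and what the comparator can show.

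**For most participants the contrast is coherent.** The synopsis and section 4.1 describe the naive cohort as receiving priming and boosting together. On the synopsis figures that cohort is 30/(30+17) = 64% to 45/(45+17) = 73% of the sample if the other cohort fills. Unvaccinated controls suit that package. This stands: for the naive cohort the problem is the boost wording and an OS clock that starts at the first boost.

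**The controls may not be unvaccinated.** Section 5.1 does not say that they are. Parent-trial participants also had surgery and adjuvant chemoradiation at this institution, so the matching factors do not exclude them, and citation 5 cannot be traced in an unnumbered reference list. This stands too. A reader might infer a planned comparison against strictly unvaccinated controls; the text supports only that vaccination is uncontrolled. A mixed control group would not isolate boosts either.

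**The background survival figures tempt one to size the bias.** Section 2.8.1 reports for the phase II parent trial: "The one and two year survival rates are 88% and 76%, respectively" (section 2.2 gives 78% at two years). With exponential survival, S(t) = 0.5^(t/median), the 18-month median in section 2.6 gives 63.0% and 39.7% at 12 and 24 months, so gaps of 25 and 36 points. The 24-month median gives 70.7% and 50.0%, so gaps of 17 and 26 points. A reader might infer that this much would be credited to boosts. The documents do not support that:

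- The parent-trial patients were not selected for a recurrence-free year, and their survival is not on the first-boost clock.
- The medians are cited background figures, not the matched controls of section 5.1, and the 24-month one covers all malignant pancreas tumors.
- The one- and two-year rates rest on different evaluable sets (56 and 36 patients), so 76/88 is not a proper conditional survival.
- The phase II course itself had a fifth vaccine six months after the fourth, so it is not a clean unboosted benchmark.
- Exponential survival is an assumption.

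**Conclusion.** The point holds as a mismatch between objective and comparator. Following the plan cannot yield a boost-specific efficacy estimate, because all participants are vaccinated before boosting and the controls are not matched on vaccination. In the vaccine-naive cohort this is mainly a labelling conflict. In the previously vaccinated cohort the comparison does not answer objective 2, and the recurrence-free year adds selection that the matching does not address.

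The size cannot be computed from the documents. The 0.9 to 0.5 range is an assumption about the earlier course and shows only the mechanism. A reader might also infer that the plan itself attributes the whole contrast to boosts. It does not say so; the risk arises because objective 2 and section 4.3.1 define efficacy in terms of boosts while section 5.1 supplies a comparator that cannot separate them.

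**What to change.** In sections 5.1 and 4.3.1 and in objective 2:

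- **Vaccine-naive cohort.** Report the comparison with historical controls as the effect of the prime-plus-boost regimen. Time both OS and PFS from the first vaccine. Starting OS at the first boost leaves out anyone who recurs during or after priming and so never qualifies for a boost.
- **Previously vaccinated cohort.** Report it without comparison to those historical controls. Optionally, compare descriptively with parent-trial participants who were recurrence free and unboosted at the same time since their last vaccine, but only if enough exist and their follow-up is available. State selection as a limitation. The group may be very small: section 4.1 counts 17 potentially eligible patients and section 3.2 counts 18, against a cohort limit of 17. Long-term follow-up under J0248 also needs separate consent.
- **Objective 2.** Reword it so that no boost-specific efficacy is claimed from the historical-control comparison.

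The cost is wording plus, if feasible, a descriptive analysis of parent-trial and J0248 follow-up data. No new patients, visits or procedures are needed. The downside is a narrower efficacy claim.

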5.2 Evaluation of Immune Responses

A central goal of the clinical trial is to identify immunologic changes associated with the vaccine therapy that may be markers of potential clinical responses. The local immune response to vaccine will be tested with biopsy and histological analysis. Specific systemic responses to tumor and to normal tissue will be assessed by in vitro assays.

The leukapheresis product or peripheral blood will be obtained from each research participant at periodic protocol-specified intervals for the in vitro assays. In addition, research participants may be asked to donate additional lymphocytes by leukapheresis. Informed consent will be obtained for this procedure using the Leukapheresis Informed Consent Form which is a separate document than the main vaccine study informed consent form.

De-identified samples may be shared with other investigators with written authorization from the principal investigator. Additional samples may be collected for research purposes, including, but not limited to those obtained through biopsies, surgeries, and autopsies.

5.2.1 In vitro analysis of induction of antitumor immunity

Autologous lymphocytes will be obtained from peripheral blood before the first and each semi-annual vaccination for in vitro immune monitoring studies. Approximately 200 ml of blood will be required at these time points for all of the following immunologic studies. Studies include the analysis of pancreatic adenocarcinomas for: (1) shared tumor-specific antigens, (2) k-ras specific antitumor immune responses. Twenty ml of blood will be obtained prior to each vaccination for serum banking.

5.2.2 Biopsy of Vaccine Site

Patients will be observed for signs of local inflammation and induration. If responses in this trial are similar to the responses observed in the Phase I and II allogeneic pancreatic tumor vaccine studies, marked inflammatory responses will be present between days 1 and 3. A baseline 3 mm punch biopsy will be obtained for vaccine naïve research participants only. Additional skin biopsies may be obtained, if clinically indicated. Vaccine sites may be photographed before injections and before biopsies. The biopsy sites will be anesthetized with local 1% lidocaine with 1:100,000 epinephrine.

Half of the biopsy specimen will be formalin fixed for hematoxylin and eosin stains. The other half of each biopsy specimen will be snap frozen in OCT for immunohistochemistry stains including; T cell staining (antiCD3), macrophage staining (Ham56), dendritic cell staining (S100), B cell staining (antiCD20), and cytokeratin staining (for presence of tumor cells).

To semiquantitate the immune infiltration, the slides will be interpreted without knowledge of the research participant's information. The type of immune cells infiltrating the vaccine site adjacent to the vaccine cells will be determined using the immunohistochemical stained slides. In addition, a semiquantitative estimate of the proportion of each infiltrating cell type will be determined using a grid to count the number of each cell type per number of tumor cells in that field. These methods for semiquantitation have been successfully employed in the renal vaccine trial. These results will be compared with the biopsy results from our previous vaccine trials.

The biopsy of the vaccine site should not significantly jeopardize any potential therapeutic benefit for the patient. The amount of vaccine and the number of responding immune cells removed by this biopsy is believed to be small.

5.3 Evaluation of psychosocial and symptom responses

There is a gap in the literature regarding the psychosocial and symptom profiles of long-term cancer survivors. For a cancer, such as pancreatic cancer, that has a dismal prognosis, the information gained through intermittent evaluations of research participants' quality of life, trust, hope, social support, decisional control preferences, advance directive preferences, and symptoms will be quite valuable. Due to limited research, the data collected through this study may bring forth new insights into the quality of life of people who are out living their expected survival time.

The surveys and measurement tools will be completed at days 0 and 28 while the research participant is physically at Johns Hopkins, if possible. On day 0, the goal is to have the forms completed prior to vaccination, but in order to minimize subject burden the forms may be completed during the monitoring period immediately after vaccination. If the participant has a visit scheduled at Hopkins, the day 28 surveys will be completed during the visit. If the participant is unable to complete the surveys during the day 0 or 28 visit they will be asked to return the surveys when completed. A stamped return addressed envelope will be provided if the participant is unable to complete the surveys at the visit, and a deviation from the standard timing will be noted.

The psychosocial and symptom responses will be measured through:

EORTC QLQ-C30

City of Hope Quality of Life, Cancer patient/survivor version, QOL-CA

Herth Hope Index

Symptom Distress Scale

Trust Scale

Pancreatic Cancer Survivor Survey

The European Organization for Research and Treatment of Cancer (EORTC) QLQ-C30 version 3 is a likert-scale evaluation of 30 items that focuses on physical activities, symptoms, overall health and overall quality of life.

The Quality of Life Scale: Patient/Cancer Survivor (QOL-CS) Version measures the quality of life (QOL) in people with cancer through a 41 item interval level scale. This QOL instrument has been used extensively in cancer survivorship research studies. It measures an overall QOL that has a Cronbach's alpha coefficient of 0.93, as well as four domains contained within QOL: physical, psychological, social, and spiritual well-being with subscale alphas of 0.71, 0.77, 0.81, and 0.89, respectively (Ferrell, Hassey-Dow & Grant, 1995, Ferrell, Hassey-Dow, Leigh, Ly, & Gulasekaram, 1995).

The Herth Hope Index is a four-point Likert scale with 12 items related to the concept of hope in this instrument developed by Herth (1991, 1992) that provides a score of 12 to 48, with a higher value indicating a higher level of hope.

The Symptom Distress Scale is a symptom burden assessment instrument developed by McCorkle and Young (1978) that measures the frequency and intensity of nausea and pain (2 items for each symptom), and a single measure of appetite, insomnia, fatigue, bowel, concentration, appearance, breathing, outlook, and cough on a five point Likert- like scale

The Patient Trust Scale is a 10 item survey strongly related to patient satisfaction and medical care ($r = 0.68$, $P < 0.0001$). It covers three dimensions: honesty, confidentiality, competency, and agency (Kao, Green, Zaslavsky, Koplana, & Cleary, 1998).

The Pancreatic Cancer Survivor Survey Research Participant Baseline Survey is being pilot tested in this clinical research study. The survey questions research participants on issues not covered in the previous established measurement tools, such as: research participation decision making, conflict of interest, informed consent, and advance directives.

